4.1.1 Treatment overview (Cohorts 1 & 2)

After being consented, patients will undergo baseline evaluations including clinical exam, complete blood count, blood chemistry, and thyroid function test. Baseline core or surgical biopsy and images with either CT scan or MRI scan will be obtained at screening. Blood collection for correlative analyses will be performed anytime after consent and prior to Nivolumab administration. Nivolumab 480mg will be administered intravenously on approximately Day -28 prior to planned surgery on Day 0 to Day +14 (14 day window as needed for scheduling surgery/logistics). An earlier surgery date is permissible if clinically indicated – see section 4.1.2 (salvage treatment).

Patients will undergo post-treatment images and specimen collection ideally within 7 days from planned surgery date, or as clinically indicated.

Post-operative adjuvant treatment with radiotherapy or chemoradiotherapy can be delivered, if clinically indicated at the discretion of treating physician following the standard of care. All subjects will

Johns Hopkins Protocol #: J1923

get follow up imaging about 3 months after completion of curative therapy (e.g. after adjuvant therapy) as per clinical routine.

After the initial post-treatment images, further imaging will be obtained as clinically indicated. In case of recurrence, a biopsy will be obtained and the specimen will be secured for future analyses if clinically feasible.

To explore oral and gut microbial correlates of response to neoadjuvant nivolumab, stool samples and oral rinses will be collected at baseline prior to infusion and then again prior to surgery. Subjects will also be asked to fill out a medical, antibiotic use and dietary questionnaire that will be used to assess whether antibiotic use or dietary patterns correlate with features of the oral and gut microbiome.

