4.10 Study calendar

| Procedure | Screening (Days -42 to -29) ^a | Day -28 | Pre- surgical evaluation (Days -7 to -1)** | Day 0 Surgery (up to day +14) | Post- surgical evaluation (Days 21 to 42) | Follow-up visits (Every 3-4 months for 1 yr; then every 6 months for 2nd yr.) ^{\$\$} | At the time of recurrence | Survival Follow-up (every 12 months) |
|--|--|------------|--|---|---|---|---------------------------------|---|
| Clinical Assessments | | | | | | | | |
| Physical Exam | X | X | X | | X | X | X | |
| Vital Signs | X | X | X | | X | X | X | |
| Performance status (ECOG) | X | X | X | | X | X | X | |
| Concomitant medicines | X | X | X | | X | X | X | |
| Toxicity assessments | X | X | X | | X | X | X | |
| Electrocardiogram (EKG) | X | | | | | | | |
| Laboratory Tests | | | | | | | | |
| CBC with diff | X | X**** | X | | X | X | X | |
| Chemistry including LFT | X | X**** | X | | X | X | X | |
| # IF abnormal LFTs draw: Hepatitis B/C serology | (X) [#] | | | | | | | |
| TSH | X | | | | X | X | | |
| Free T4 and T3 | X | | | | | | X | |
| PT/INR and PTT | X | | X | | | | X | |
| Pregnancy Tests (WOCBP only) | X | | X | | X | | X | |
| Treatment | | | | | | | | |
| Nivolumab | | X | | | | | | |
| CT neck/chest with IV contrast* | X | | X | | | (X) | (X) | |
| MRI neck with IV contrast, optional† | (X) | | (X) | | | (X) | (X) | |

| Procedure | Screening (Days -42 to -29) | Day -28 | Pre- surgical evaluation (Days -7 to -1) | Day 0 (and up to day +14) Surgery | Post- surgical evaluation (Days 21 to 42) | Follow-up visits (Every 3- 4 months for 1 yr; then every 6 months for 2nd yr.) ^{§§} | At the time of recurrence | Survival Follow-up (every 12 months) |
|---|-----------------------------------|----------------|--|---|---|---|---------------------------------|---|
| Correlative Blood/Tissue/Stool Studies | | | | | | | | |
| PBMCs, Serum, plasma (Blood collection 100 cc's) | | X ^b | | X | X | X | X | |
| Tumor biopsy/sample | X | | | X (resection specimen) | | | X | |
| Stool Sample | | X ^c | X | | X | X | X | |
| Oral Rinse ^d | | X | | | X | X ^d | X | |
| Medical & Dietary Questionnaire | | X | | | X | X | X | |
| Survival | | | | | | | | X |

- a. screening labs are permitted to be used for treatment if completed within three (+3) days of day -28
- b. Research blood permitted to be collected anytime after consent and prior to Nivolumab infusion (Days -42 to day -28)

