We will consider using 16S rRNA, shotgun metagenomics and/or RNA-seq for analyses. 16S rRNA sequencing data will be filtered for poor quality and contaminant/chimeric sequences, followed by taxonomic assignment using standard bioinformatic pipelines such as QIIME and Resphera Insight. To detect differentially abundant taxa between responders and non-responders, we will utilize the nonparametric Mann-Whitney test with correction for multiple hypothesis testing using the False Discovery Rate. To evaluate beta-diversity between responders and non-responders (i.e. shared total community composition), we will compute the UniFrac distance metric for all sample pairs, followed by principal coordinate analysis and significance testing with PERMANOVA⁵⁰. Functional inference of gene content from 16S rRNA data may also be performed using tools such as PICRUSt. While 16S rRNA identifies only bacterial sequences, metagenomics permits detection of viruses and fungi among others. Metagenomic analyses will be designed to remove human contaminant sequences followed by taxonomic assignment using Kraken and Pathoscope. Functional characterization of metagenomic data will be performed using the HUMAnN tool. Additionally, RNA-seq analysis (meta-transcriptomics) enables characterization of actively transcribed microbial genes and RNA viruses, with the potential to explore the combined host:microbial interaction(s).

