Never drank after age 40 _____

Currently aged less than 40 years _____

MEDICAL QUESTIONS

23. Have you taken antibiotics in the last 3 months? Yes No

A list of antibiotics is attached for you to refer to. If no, skip to question 25.

24. If you know the name of the antibiotic(s), please write it here.

25. Have you had a bronchoscopy in the last 3 months? Yes No

26. Have you taken oral corticosteroids in the last 2 weeks? Yes No

(Oral corticosteroids examples: prednisone, dexamethasone, methylprednisolone, hydrocortisone)

27. If you answered Yes to (26), please write the name and dose here and when you took these.

28. Have you taken inhaled corticosteroids in the last 2 weeks? Yes No

(Inhaled corticosteroids examples: budesonide, fluticasone, beclomethasone, ciclesonide)

29. If you answered Yes to (28), please write the name and dose here and when you took these.

30. Do you have sleep apnea? Yes No

31. Do you have reflux disease? Yes No

32. Do you have any other chronic lung conditions? Yes No

33. If you answered Yes to (32), please write the name of the condition here

DENTAL HEALTH

34. About how often do you visit a dentist?

- Less than every 6 months.
- Between every 6-12 months.
- Greater than every 12 months.
- I have never been to a dentist.

35. Overall, how would you rate the health of your teeth and gums?

Excellent Good Fair Poor

36. Have you ever had treatment for gum disease such as scaling and root planing, sometimes called deep cleaning? Yes No

37. Have you ever had any teeth become loose on their own, without an injury? (Not including baby teeth). Yes No

DIET QUESTIONS

38. Do you eat meat? Meat is defined as beef, chicken, pork, lamb or venison:

- A. I do not eat meat.
- B. I have eaten meat in the last year.
- C. I have eaten meat one or more times a month during the last year.
- D. I have eaten meat one or more times a week during the last year.

39. Do you eat Fish? Fish is defined as all fish and shellfish:

- A. I do not eat fish.
- B. I have eaten fish in the last year.
- C. I have eaten fish one or more times a month during the last year.
- D. I have eaten fish one or more times a week during the last year

40. Do you eat Eggs?

- A. I do not eat eggs
- B. I have eaten eggs in the last year
- C. I have eaten eggs one or more times a month during the last year
- D. I have eaten eggs one or more times a week during the last year

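### The planned baseline microbiome-response tests take no account of recent antibiotic use, which the trial plans to collect; an antibiotic-stratified companion analysis should be added beside them

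*Combined protocol and SAP*

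**What the plan says.** Section 11.2.2 plans two comparisons by response status.

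- **Per taxon:** "To detect differentially abundant taxa between responders and non-responders, we will utilize the nonparametric Mann-Whitney test". Multiplicity across taxa is handled by FDR, at a level that is not given.
- **Whole community:** UniFrac distances, "followed by principal coordinate analysis and significance testing with PERMANOVA".

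Neither names a covariate, a stratum or a sensitivity analysis, and the section does not say which sample time enters the comparison.

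Antibiotic exposure is to be collected. Section 4.1.1 states: "Subjects will also be asked to fill out a medical, antibiotic use and dietary questionnaire". The study calendar (section 4.10) places the questionnaire at Day -28, the visit of the baseline stool sample and oral rinse. Item 23 of the initial form in Appendix D asks: "Have you taken antibiotics in the last 3 months". The stated use is narrow. The answers are to be "used to assess whether antibiotic use or dietary patterns correlate with features of the oral and gut microbiome". Nothing carries them into the responder comparison.

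Section 1.2 lists the microbiome work under exploratory aims, and section 11.2.2 also describes it as exploratory and correlative.

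**The concern.** Antibiotics taken in the 3 months before the baseline questionnaire come before both the baseline sample and the response. Section 4.1.1 already treats them as a possible influence on the microbiome. If patients with recent antibiotics also respond less often, for example because they had infections or worse disease, the two response groups contain different proportions of exposed patients. A taxon shifted by antibiotics then tends to differ between the groups even if it plays no part in response.

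FDR control does not cure this. It deals with the number of taxa tested and takes each p-value as valid. Here the p-values themselves would be too small.

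What is at stake is how the exploratory hits are read. The purpose of the analysis is to relate oral and gut communities to response, and the planned tests alone cannot separate that from past antibiotic exposure.

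**Working it through.** The plan gives no power or error rate for the microbiome analysis, so there is no figure to reproduce. The check is a simulation under stated assumptions.

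**Inputs from the documents.** Section 10.2 expects 12 patients per cohort (24) and allows up to 26 in total. The tests are those of section 11.2.2. Section 2.3 reports major pathologic response in 9 of 20 resected lung tumors (45%); using that as a guide to the responder share here is an assumption.

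**Assumed.** Antibiotic prevalence, response by exposure, and an antibiotic effect on the taxon of 1 to 2 SD. Given antibiotic use, the taxon is independent of response.

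**Why bias can arise.** The mean difference between response groups equals the antibiotic shift times the difference in exposure between non-responders and responders. With 25% exposed and response 45% unexposed against 10% exposed:

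- overall response = 0.75 × 0.45 + 0.25 × 0.10 = 0.3625
- exposed among responders = 0.025 / 0.3625 = 6.9%
- exposed among non-responders = 0.225 / 0.6375 = 35.3%
- difference = 28.4 points, so shifts of 1 and 2 SD give group differences of 0.28 and 0.57 SD.

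If response does not depend on exposure, the difference is zero.

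**Tests compared.** Two-sided Mann-Whitney at 0.05 per taxon before FDR, and the van Elteren test stratified by antibiotic use. The latter is z = T / √V, with T = Σ w(W − n₁(n+1)/2), V = Σ w² n₁n₀(n+1)/12 and w = 1/(n+1). Sums run over strata; W is the responders' rank sum, and n₁, n₀ and n are the responders, non-responders and total in the stratum.

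**Result 1: response rates set by exposure** (n = 24, 4,000 trials per scenario, at least 3 patients per response group, shift 1 to 2 SD).

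| Response, unexposed vs exposed | Exposed | Mann-Whitney false positives |
|---|---|---|
| equal (30% vs 30%) | 25% or 40% | 4.0-5.0% |
| 40% vs 20% | 25% or 40% | 5.4-9.3% |
| 45% vs 10% | 25% | 8.0-13.2% |
| 45% vs 10% | 40% | 10.8-21.3% |

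The stratified test gives 4.0-5.2% throughout. Across repeated runs of the unequal-response scenarios, the unadjusted rate spans about 6-23%.

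**Result 2: exposure rates set by response group** (11 responders of 24, or 12 of 26; 4,000 trials per scenario).

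| Exposed: responders vs non-responders | 1 SD, n = 24 / 26 | 2 SD, n = 24 / 26 |
|---|---|---|
| 30% vs 30% | 4.7% / 4.8% | 5.0% / 4.6% |
| 20% vs 40% | 6.8% / 6.7% | 9.9% / 9.8% |
| 10% vs 50% | 13.6% / 14.0% | 27.7% / 30.4% |
| 5% vs 60% | 20.4% / 21.8% | 49.9% / 52.7% |

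The stratified test gives 4.6-5.5%. The last row is an extreme case: with 11 responders of 24 it implies response of 0.55 / (0.55 + 7.8) = 6.6% in exposed patients against 10.45 / (10.45 + 5.2) = 66.8% in unexposed patients.

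**Result 3: cost of stratifying if the taxon is on the pathway.** Antibiotics lower the taxon, and the taxon alone drives response (logit slope 1.2 per SD, intercept -0.2; n = 24; 2,000 trials; all assumed).

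| Exposed | Shift | Power, Mann-Whitney | Power, van Elteren | Loss |
|---|---|---|---|---|
| 25% | 1 SD | 67% | 56% | 11 points |
| 25% | 2 SD | 78% | 55% | 23 points |
| 40% | 1 SD | 68% | 54% | 14 points |
| 40% | 2 SD | 81% | 49% | 32 points |

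**Result 4: sparse strata.** With response 45% vs 10%, the exposed stratum is empty or holds only one response class in 52-56% of trials at 25% exposed, and in 37% at 40% exposed. The stratified test then uses unexposed patients only.

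PERMANOVA and error rates after FDR were not simulated.

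**The case against.** The strongest objection is causal. Antibiotics may lower response by altering the microbiome, and section 11.2.2 itself cites work suggesting that microbiome composition affects response. The unadjusted association is then real, and stratifying discards part of it. Result 3 bears this out: the loss is 11 to 32 points. This stands, and it rules out making the stratified test the main test by default.

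Second, the bias is conditional. The documents give no antibiotic prevalence, no response rate by exposure and no effect size. This also stands. A reader might infer that every taxon altered by antibiotics will be reported as response-linked, or that the planned tests are invalid. The documents support neither. Even in the unequal-response scenarios of Result 1, such a taxon is flagged in a minority of trials before FDR, and with equal response there is no excess.

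Third, the correlation planned in section 4.1.1 would show which taxa are sensitive to antibiotics. That helps interpretation, but it leaves the response comparison unchanged.

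Fourth, smoking, diet, cohort and HPV status could also confound, and 26 patients cannot support strata for all of them. That is a fair limit on how much to adjust. Antibiotics are not an arbitrary choice, however: section 4.1.1 names them, with diet, as a factor to relate to the microbiome.

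Finally, it is tempting to say that antibiotic use will be known for every patient. The plan is to ask each subject, so the data are self-reported and may be incomplete.

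**Conclusion.** The point holds as a gap in an exploratory analysis. The baseline responder comparisons ignore antibiotic use, although the plan collects it and treats it as related to the microbiome. If antibiotic use differs by response, the per-taxon false-positive rate at a nominal 5% rises to about 6-23% with 24 patients, and higher only under more extreme imbalance. If it does not differ, the rate stays near 5%. These figures rest on assumed exposure rates, response rates and effect sizes.

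Replacing the planned tests is not justified, because the documents cannot settle whether antibiotics confound the association or act through the taxon. Showing both analyses lets the reader see how far a hit depends on antibiotic exposure. No primary or secondary endpoint, sample size or stopping guideline is affected.

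**What to change.** Keep the Mann-Whitney test with FDR and the PERMANOVA. For the baseline sample, add to section 11.2.2 a pre-specified companion analysis:

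1. a van Elteren test per taxon, stratified by item 23 (yes/no);
2. PERMANOVA with antibiotic use entered before response, or with permutation within antibiotic strata;
3. the responder comparison restricted to patients without antibiotics in the last 3 months.

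State that a taxon will be described as response-linked independently of antibiotics only if its direction and approximate size persist in these analyses. Loss of significance alone should not be read as confounding, because the companion tests have less power (roughly 10-30 points lower if antibiotics act through the taxon). With few exposed patients, the first analysis will often reduce to the third. Report the number exposed in each response group so that this is visible.

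Confine the change to the baseline sample. The calendar has no questionnaire at the pre-surgical visit, so antibiotic use between Day -28 and that sample would have to come from the concomitant medicines recorded there.

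The cost is a few sentences of text and some extra output, with no new data or visits. The wording should be settled before response status is linked to the sequencing data, so that the adjustment is not chosen after the fact.

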Appendix A. ECOG Performance Status Scale

| Score | Definition |
|-------|---|
| 0 | Asymptomatic |
| 1 | Symptomatic, fully ambulatory |
| 2 | Symptomatic, in bed less than 50% of day |
| 3 | Symptomatic, in bed more than 50% of day, but not bedridden |
| 4 | Bedridden |

Appendix B. Guidelines for Tissue Banking Process (may be modified based on guidelines in correlative SOP, which will be continually updated)

Note: Only tissue that is absolutely not needed for clinical diagnosis or staging should be collected for tissue banking. If in doubt about this, do NOT submit specimens for banking.

Banking of Frozen Tissue

1. Place a single tissue specimen flat in the plastic bag. A single tissue specimen's overall volume should be at least 1 cm³, and at most 3–4 cm³, with at least one dimension measuring 0.5 cm thick or less to facilitate quick freezing.
2. For a given case (patient), please collect sufficient non-malignant and malignant tissue. Tissue selected should be grossly viable, and grossly consistent with tumor or adjacent normal tissue (see #5 below for contraindications). Non-malignant (i.e. "adjacent normal") tissue should be collected at least 2 cm from the primary tumor, subject to any limitations from the specimen's physical dimensions. Do not place tumor and non-malignant tissue in the same bag. For large tumors, do not place large pieces of tissue in a single bag. Rather, divide the tissue according to size guidelines in #1 above, and place each in an individual bag. Collect and separately identify both: 1) primary tumor and 2) metastatic lesions to lymph nodes or other tissues. Tissue will typically be taken by scalpel or dissection blade, though the use of 5 -7 mm skin punch biopsy tools could be considered in certain situations.
3. Immediately place the specimens for freezing in an isopentane or 2-methylbutane cryobath, or other effective liquid freezing agent. If no cryobath is available, then liquid N₂ can be used as the freezing agent, in a properly insulated container and with sufficient safety precautions. The goal is to have bankable tissue immersed in the bath within 30 minutes of the OR's procurement from the patient. If more cryobath space is needed, move already frozen tissue to a -80C freezer in order to make sufficient room. Make sure to check periodically for cryobath problems (e.g. not maintaining temperature, refrigerant level low), and call for appropriate maintenance as needed. Do not freeze tissue by placing it fresh directly in the -80C freezer.
4. On receipt by the tissue bank laboratory, the frozen tissue is embedded in OCT (Optimal Cutting Temperature medium), and a frozen section is stained with H&E and the section evaluated by the tissue bank pathologist for quality assurance (QA) purposes. A report on the histopathologic findings is filed or communicated as needed. The frozen section evaluation can also count for adjacent pieces of tissue if they were taken as a "mirror image" section to the surface cut for the frozen section.
5. General contraindications to tissue banking

DON'T bank tissue from these specimen types or situations:

- small tumors and other cases where all or most of the lesional tissue is needed for diagnosis
- surgical margins of resection specimens where tumor and benign areas cannot be clearly delineated grossly grossly visible areas of primarily necrosis, hemorrhage, or fat
- specimens which are known to have been delayed significantly more than 30 minutes past their procurement time in the OR
- tissue previously freeze-thawed, or frozen slowly (e.g. in the cryostat or -80 freezer)
- areas of deepest invasion, tumor/normal interface, tumor/capsule interface, extranodal extension of tumor, and other key landmarks needed for surgical pathology evaluation and/or tumor staging
- diagnostic biopsies where most or all tissue must be submitted for pathology evaluation: most lymph node, GI, bone marrow, and liver biopsies fall in this category
- tissue clearly marked as intended for a special study such as immunofluorescence

Appendix C. Immune-Related Adverse Events Management Algorithms

These general guidelines constitute guidance to the Investigator and may be supplemented by discussions with the Principal Investigator. The guidance applies to all immuno-oncology agents and regimens.

A general principle is that differential diagnoses should be diligently evaluated according to standard medical practice and SITC or ASCO irAE management guidelines should be consulted . Non-inflammatory etiologies should be considered and appropriately treated.

Corticosteroids are a primary therapy for immuno-oncology drug-related adverse events. The oral equivalent of the recommended IV doses may be considered for ambulatory patients with low-grade toxicity. The lower bioavailability of oral corticosteroids should be taken into account when switching to the equivalent dose of oral corticosteroids.

Consultation with a medical or surgical specialist, especially prior to an invasive diagnostic or therapeutic procedure, is recommended.

The frequency and severity of the related adverse events covered by these algorithms will depend on the immuno-oncology agent or regimen being used.

Appendix D: Sociodemographic questionnaires (Initial and follow-up)

Initial Sociodemographic Characteristics Questionnaire

Date: Month _____ / Day _____ / Year _____

Study ID Number: _____

Medical Records Number: _____

SOCIODEMOGRAPHIC CHARACTERISTICS QUESTIONNAIRE

1. Name: _____

2. Birthdate: month _____/day _____/year _____

3. Sex: Male Female

4. What is your race or ethnic group? Caucasian Hispanic African American
 Asian Other _____
 I choose not to disclose

FAMILY QUESTIONS

Both genetics and environment could be risk factors for the development of cancer. For this reason, it is important to determine your biological relationship with your family.

5. Are you adopted? Yes No

6. How many of each of the following family members do you have?

Brothers: _____ Sisters: _____ Sons: _____ Daughters: _____

SMOKING QUESTIONS

7. Do you smoke cigarettes? Yes No, never
 Not currently but I have in the past

8. At what age did you start smoking? _____

9. When did you quit smoking cigarettes? _____

10. How many total years have you or did you regularly smoke cigarettes? _____

11. During the time you usually smoked regularly, how many cigarettes do or did you usually smoke per day? _____

12. Do you smoke cigars? Yes No, never Not currently but I have in the Past

13. At what age did you start smoking cigars? _____

14. When did you quit smoking cigars? _____

15. How many years in total did you regularly smoke cigars? _____

16. Do you use smokeless tobacco or other nicotine products? (i.e. chewing tobacco, snuff, e-cigarette, nicotine patch or gum) Yes No

If yes, please indicate type(s): _____

17. Were you exposed to asbestos, that you know of? Yes No

18. Were you exposed to any other potential harmful exposures to your lung? Yes No/never

ALCOHOL QUESTIONS

19. Have you ever drunk alcoholic beverages, such as beer, wine, or liquor regularly, that is at least once a month? Yes No

20. At what age did you start drinking alcoholic beverages regularly, i.e. at least once a month? _____ years of age

21. Before the age of 40, how many drinks of beer (12 oz.), wine (5oz.), or liquor (1 oz.) did you usually drink per week?

More than one per week. Please indicate number _____

Less than one per week _____

Never drank before age 40 _____

22. After the age of 40, how many drinks of beer (12 oz.), wine (5 oz.), or liquor (1 oz.) did you usually drink per week?

More than one per week. Please indicate number _____

Less than one per week _____

Never drank after age 40 _____

Currently aged less than 40 years _____

MEDICAL QUESTIONS

23. Have you taken antibiotics in the last 3 months? Yes No

A list of antibiotics is attached for you to refer to. If no, skip to question 25.

24. If you know the name of the antibiotic(s), please write it here.

25. Have you had a bronchoscopy in the last 3 months? Yes No

26. Have you taken oral corticosteroids in the last 2 weeks? Yes No

(Oral corticosteroids examples: prednisone, dexamethasone, methylprednisolone, hydrocortisone)

27. If you answered Yes to (26), please write the name and dose here and when you took these.

28. Have you taken inhaled corticosteroids in the last 2 weeks? Yes No

(Inhaled corticosteroids examples: budesonide, fluticasone, beclomethasone, ciclesonide)

29. If you answered Yes to (28), please write the name and dose here and when you took these.

30. Do you have sleep apnea? Yes No

31. Do you have reflux disease? Yes No

32. Do you have any other chronic lung conditions? Yes No

33. If you answered Yes to (32), please write the name of the condition here

DENTAL HEALTH

34. About how often do you visit a dentist?

- Less than every 6 months.
- Between every 6-12 months.
- Greater than every 12 months.
- I have never been to a dentist.

35. Overall, how would you rate the health of your teeth and gums?

Excellent Good Fair Poor

36. Have you ever had treatment for gum disease such as scaling and root planing, sometimes called deep cleaning? Yes No

37. Have you ever had any teeth become loose on their own, without an injury? (Not including baby teeth). Yes No

DIET QUESTIONS

38. Do you eat meat? Meat is defined as beef, chicken, pork, lamb or venison:

- A. I do not eat meat.
- B. I have eaten meat in the last year.
- C. I have eaten meat one or more times a month during the last year.
- D. I have eaten meat one or more times a week during the last year.

39. Do you eat Fish? Fish is defined as all fish and shellfish:

- A. I do not eat fish.
- B. I have eaten fish in the last year.
- C. I have eaten fish one or more times a month during the last year.
- D. I have eaten fish one or more times a week during the last year

40. Do you eat Eggs?

- A. I do not eat eggs
- B. I have eaten eggs in the last year
- C. I have eaten eggs one or more times a month during the last year
- D. I have eaten eggs one or more times a week during the last year

41. Do you eat Cheese? (This includes fresh, soft, aged or cottage cheese as well as sour cream):

- A. I do not eat cheese
- B. I have eaten cheese in the last year
- C. I have eaten cheese one or more times a month during the last year
- D. I have eaten cheese one or more times a week during the last year

42. Do you drink Milk? Milk is defined as milk from a cow, goat or sheep (not soy, coconut or almond milk, for example). If you put milk on your cereal, you should not answer (A).

- A. I do not drink milk
- B. I drank milk in the last year
- C. I drank milk one or more times a month during the last year
- D. I drank milk one or more times a week during the last year

43. Do you eat yogurt?

- A. I do not eat yogurt
- B. I have eaten yogurt in the last year
- C. I have eaten yogurt one or more times a month during the last year
- D. I have eaten yogurt one or more times a week during the last year

44. Do you take probiotics (live bacteria supplement)? Yes No

If yes (question 44) and if you know the name of the probiotic product(s), please write here:

45. Do you take vitamin supplements?

Yes No

If yes (question 45) and if you know the name of the vitamin supplement(s), please write it/them here:

WORK AND PHYSICAL ACTIVITY

46. What is your current employment status?

Employed/self-employed Unemployed Retired Disabled

47. How would you categorize your physical activity on the job?

Mostly sedentary or light activity (e.g. mostly sitting, standing, lifting light objects of less than 3 kilos).

Mostly medium activity (e.g. much walking, climbing stairs).

Mostly intense activity (e.g. heavy construction work).

Unemployed/retired/disabled

48. What type of exercise (physical activity) do you do regularly (at least 3 times per week)?

Mostly moderate activity (slow walking, gardening, golfing etc.)

Mostly vigorous activity (running, swimming, bicycling, football etc.)

I do not exercise regularly

49. At age 20, what type of exercise did you do regularly (at least 3 times per week)?

Mostly moderate activity (slow walking, gardening, golfing etc.)

Mostly vigorous activity (running, swimming, bicycling, football etc.)

I did not exercise regularly

Follow-Up Sociodemographic Characteristics Questionnaire

Date: Month _____ / Day _____ / Year _____
Study ID Number: _____
Medical Records Number: _____

SMOKING QUESTIONS

1. Are you currently smoking? Yes No

If yes, how many cigarettes/day? _____

ALCOHOL QUESTIONS

2. Regularly? Yes No

If yes, please indicate pattern:

More than one per week _____ (If checked), please indicate number _____

Less than one per week _____

MEDICAL QUESTIONS

3. Have you taken antibiotics since completing the last questionnaire? Yes No

4. If you know the name of the antibiotic(s), please write it here.

A list of antibiotics is attached for you to refer to. If no, skip to question 5.

5. Have you had a bronchoscopy since completing the last questionnaire? Yes No

6. Have you taken oral corticosteroids since completing the last questionnaire? Yes No
(Oral corticosteroids examples: prednisone, dexamethasone, methylprednisolone, hydrocortisone)

7. If you answered Yes to (6), please write the name and dose here and when you took these.

8. Have you taken inhaled corticosteroids since completing the last questionnaire?

Yes No (Inhaled corticosteroids examples: budesonide, fluticasone, beclomethasone, ciclesonide)

9. If you answered Yes to (8), please write the name and dose here and when you took these.

DIET QUESTIONS

10. Do you eat meat? Meat is defined as beef, chicken, pork, lamb or venison:

- A. I do not eat meat.
- B. I have eaten meat in the last year.
- C. I have eaten meat one or more times a month during the last year.
- D. I have eaten meat one or more times a week during the last year.

11. Do you eat Fish? Fish is defined as all fish and shellfish:

- A. I do not eat fish.
- B. I have eaten fish in the last year.
- C. I have eaten fish one or more times a month during the last year.
- D. I have eaten fish one or more times a week during the last year

12. Do you eat Eggs?

- A. I do not eat eggs
- B. I have eaten eggs in the last year
- C. I have eaten eggs one or more times a month during the last year
- D. I have eaten eggs one or more times a week during the last year

13. Do you eat Cheese? (This includes fresh, soft, aged or cottage cheese as well as sour cream):

- A. I do not eat cheese
- B. I have eaten cheese in the last year
- C. I have eaten cheese one or more times a month during the last year
- D. I have eaten cheese one or more times a week during the last year

14. Do you drink Milk? Milk is defined as milk from a cow, goat or sheep (not soy, coconut or almond milk, for example). If you put milk on your cereal, you should not answer (A).

- A. I do not drink milk
- B. I drank milk in the last year
- C. I drank milk one or more times a month during the last year
- D. I drank milk one or more times a week during the last year

15. Do you eat yogurt?

- A. I do not eat yogurt
- B. I have eaten yogurt in the last year
- C. I have eaten yogurt one or more times a month during the last year
- D. I have eaten yogurt one or more times a week during the last year

16. Do you take probiotics (live bacteria supplement)? Yes No

If yes (question 16) and if you know the name of the probiotic product(s), please write here:

17. Do you take vitamin supplements? Yes. No

If yes (question 17) and if you know the name of the vitamin supplement(s), please write it/them here:

WORK AND PHYSICAL ACTIVITY

18. What type of exercise (physical activity) do you do regularly (at least 3 times per week)?

- Mostly moderate activity (slow walking, gardening, golfing etc.)
- Mostly vigorous activity (running, swimming, bicycling, football etc.)
- I do not exercise regularly
